### **Exploratory analyses:**

We will conduct mixed effects model analyses as described above to analyze self-regulation mechanistic outcomes, including Brief Experiential Avoidance Questionnaire (BEAQ), Difficulties in Emotion Regulation Scale (DERS-16),

Perceived Stress Scale (PSS), Self-Compassion Scale (SCS), Multidimensional Assessment of Interoceptive Awareness (MAIA-2), Nonattachment to Self Scale (NTS), Self-Critical Rumination Scale (SCRS), and Experiences Questionnaire-Decentering Subscale (EQD).

We will collect other mechanistic outcomes, including interpersonal variables related to the group as potential covariates or mediators, Group Cohesion, Attitude about group leader, interpersonal mindfulness, as measured by the Interpersonal Mindfulness Scale (IMS), and intervention expectancy as measured by the Credibility/Expectancy Survey. Adverse childhood experiences, Substance Abuse and Addiction Core Tier 1 (substance use severity and demographics), and distance from clinic will also be collected. We will also collect data on participant mindfulness using the Five Facet Mindfulness Questionnaire (FFMQ). We will collect weekly surveys about BUP adherence and drug use. We will ask about mindfulness practice dose in M-ROCC and recovery skills use in control arms. Attitudes about group leaders and group cohesion will be measured at 8, 16, and 24 weeks.

We will conduct mixed effects model analyses as described above to analyze several exploratory clinical outcomes, including *Beck Anxiety Inventory*, *Pain Catastrophizing Scale*, *Substance Craving Scale* and *CAT-MH outcomes (CAT-DI, CAT-ANX, CAT-PSY, CAT-MANIA, CAT-SUD, CAT-PTSD, CAT-SDOH)*. We will also analyze BUP non-adherence and diversion reports, as well as self-reported average daily dose of BZDs prescribed over final 12 weeks.

We will compare intervention retention at 24-weeks, which is defined as having an active BUP prescription in the past 28 days at the 24-week study visit. In the chance case of imbalance of assignment, we will add the following variables as measurable covariates in regression models since they are known to impact retention: psychiatric diagnosis, age, gender, race/ethnicity, unemployment, previous opioid treatment, Hepatitis C, childhood trauma, baseline cocaine use, and injection drug use history. We will also add any other baseline characteristics that may be significantly imbalanced after randomization. We will also include key data collected during the first 4 weeks of the intervention, i.e., BUP non-adherence, self-reported illicit opioid use.

We will also measure time to intervention discontinuation, and fit Cox proportional hazard models that model the risk of time to intervention discontinuation, comparing hazard rates across the intervention and control groups, adjusting for the covariates described above in the logistic regression. All individuals that do not discontinue the

intervention at the end of data collection will be considered to be right-censored. We will assess the Cox proportional hazards assumptions using tests of Schoenfeld residuals and by visual estimation of log-log plots of the estimated survival curves. We will also use Wald tests to test significance in intervention vs. control group hazard rate differences.

We will also conduct a minimum of 12 qualitative interviews for M-ROCC or control group completers to examine themes regarding online mindfulness delivery and to compare responses with our R21 qualitative outcomes from our in-person group model.

Because little is known about the dose effect or the impact of long term (> 8 weeks) mindfulness training, in exploratory analyses, we will evaluate the specific impact of MTPC intensive mindfulness sessions among those in M-ROCC who choose to continue their participation by joining MTPC, tracking their 24-week outcomes compared to the control arm that receives no mindfulness and participants that only did LDM. There is insufficient power to formally randomize and test this third arm that receives intensive MTPC, so we opt for this naturalistic design to provide exploratory data on dose effects (# of mindfulness sessions, total practice mins during 24-weeks,  $\geq 12$  group sessions, and participation in intensive MTPC-OD). Those who continue through MTPC are likely to differ at baseline from other study participants. Employing **propensity score (PS)** methods allows us to minimize bias by balancing the MTPC, LDM only, and control groups on observable intervention eligibility criteria and potential outcome confounders. We will consider PS approaches including weighting, matching (nearest neighbor, optimal, ratio, full), or sub-classification. We will select methods providing the best covariate balance across potential groups, graphically (range/density) and empirically (%-standardized difference in means  $\leq 10\%$ ).

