#### **9.2 Sample Size and Randomization**

##### Justification of Sample Size and Power Calculations:

This study will enroll an approximate of  $n = 236$  and maximum of  $n = 280$  participants who will sign informed consent and our power analyses have identified that we will have the sample to identify meaningful effects with an effective sample size of  $n=156$  with 78 individuals in the M-ROCC arm and 78 individuals in the control group. We expect to randomize at least 192 participants (96 M-ROCC: 96 Control) over 8 months in order to have an effective sample size of  $n=156$ . We will aim to recruit participants with an active buprenorphine prescription from providers in U.S. states approved for recruitment by the IRB to enroll patients at a rate of approximately 30 participants per month, anticipating 19% loss during screening and baseline assessments, so we can randomize approximately 24 participants each month for 8 months.

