Based on R21 urine toxicology data, we will focus our primary outcome analysis on the impact of M-ROCC on opioid use starting 12 weeks after intervention assignment. We estimate a mean of 4.67 negative tests for all illicit opioids (opiates, oxycodone, fentanyl, methadone) out of 6 random oral fluid toxicology tests conducted during the last 12 weeks in M-ROCC (SD 1.23) ( $n=78$ ) and 4.11 negative tests for all illicit opioids in the control check-in group (SD 1.27) ( $n=78$ ). We anticipate an effect size of Cohen's  $d = 0.45$  for between-group difference in percentage of monthly positive toxicology screens. Participation of  $N=192$  individuals randomized (with an effective sample size of 156 with 78 individuals in the M-ROCC arm and 78 individuals in the control group) allows for  $> 80\%$  power to detect an effect size of 0.45 for negative toxicology for all illicit opioids between M-ROCC and control arms. This power calculation was generated assuming a t-test of the difference between two means, a 1:1 intervention to control recruitment ratio, a type I error of 0.05, a two-sided comparison, and a design effect of 1.23 derived from an ICC of 0.01 with 8 group clusters with average cluster size of 24, which represents the average number of people randomized in each monthly cohort to either live-online M-ROCC or the live-online control group. This level of cluster was selected because it will encompass cohort effects. As the primary outcome will be analyzed in an intent-to-treat analysis, it is not sensitive to the number of individuals who drop out of the study after randomization. For secondary outcomes, based on pilot data and other relevant studies, we anticipate dropout from intervention in M-ROCC between 17-28% at 24-weeks and dropout in the control groups of 21-44% at 24-weeks.

In previous primary care studies, we have reported the impact of MTPC over 24 weeks on reductions in anxiety as measured by the PROMIS-ASF as  $d = -0.72$  ( $n=81$ ),  $p<0.001$  and  $d = -0.80$ ,  $p<0.001$  ( $n=136$ ). In our recent R21 pilot study, we reported significant Anxiety reductions over 24 weeks among patients with co-morbid anxiety at baseline ( $\geq 55$  at baseline) ( $p < .05$ ,  $ES = -0.556$ ). Given the

likelihood of a small effect of control on Anxiety after 4 weeks of buprenorphine treatment, we anticipate an effect size of  $d = -0.56$  for between-group change in PROMIS-ASF.

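### The exploratory retention and discontinuation models adjust for baseline predictors only when chance imbalance appears, so the model depends on the data and precision is given up

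*Combined protocol and SAP*

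**What the plan says.** The rule is in section 9.6, Exploratory analyses, in the paragraph on 24-week retention. It has four parts.

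- **Known predictors.** "In the chance case of imbalance of assignment, we will add the following variables as measurable covariates in regression models". The reason given is "since they are known to impact retention". The list is psychiatric diagnosis, age, gender, race/ethnicity, unemployment, previous opioid treatment, hepatitis C, childhood trauma, baseline cocaine use and injection drug use history. No test, threshold or alpha defines imbalance.
- **Other baseline variables.** "We will also add any other baseline characteristics that may be significantly imbalanced after randomization". Again no alpha is given.
- **Cox model for time to discontinuation.** It is fitted "adjusting for the covariates described above in the logistic regression", so it inherits the rule.
- **Early post-randomisation data.** "We will also include key data collected during the first 4 weeks of the intervention, i.e., BUP non-adherence, self-reported illicit opioid use". No imbalance condition is attached. This is a separate issue and is not pursued here.

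Section 4.3 names scheduling acceptability of the assigned group as a covariate with no imbalance condition. Section 6.2.2 describes randomisation in blocks of 4, 6 or 8 with no stratification factors. Retention and time to discontinuation are items 1 and 2 of the exploratory clinical outcomes in section 9.5.2, a family of 15 under the false discovery rate procedure.

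**The concern.** In a randomised comparison, any baseline difference between arms is chance. Whether a covariate belongs in the model depends on how well it predicts the outcome, and the plan already answers that for its ten variables. Making their use conditional on imbalance discards this information in most realisations of the trial. With no stratification described, adjustment in the analysis is the only way the trial can use it.

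The rule also leaves the model open until the data are in. The text can be read as adding each imbalanced variable, or as adding all ten once imbalance appears, and it does not say who decides or how. Odds ratios and hazard ratios are non-collapsible, so the quantity estimated changes with the covariates that happen to enter.

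At stake are the precision and reproducibility of two exploratory comparisons.

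**Working it through.** **1. Inputs.** Section 9.2: "We expect to randomize at least 192 participants (96 M-ROCC: 96 Control) over 8 months". The same section states, for the primary outcome, "a type I error of 0.05, a two-sided comparison, and a design effect of 1.23 derived from an ICC of 0.01". A 5% alpha for the balance test is carried over from there as an assumption. Dropout from intervention at 24 weeks is put at 17-28% in M-ROCC and 21-44% in control.

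**2. The plan's own figures.** The design effect is 1 + (24 - 1) × 0.01 = 1.23. Then 192 / 1.23 = 156.1, or 78 per arm, as stated. For d = 0.45 at 78 per arm, power is 80.2% by the normal formula and 79.7% by the noncentral t. The plan states no power for retention or discontinuation.

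**3. What a 5% balance test would flag.** In SD units the threshold is 1.96 × √(2/n).

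| Setting | Smallest flagged difference |
|---|---|
| n = 96, alpha 0.05 | 0.283 SD (t version 0.285) |
| n = 78 (effective), alpha 0.05 | 0.314 SD |
| n = 96, alpha 0.10 | 0.237 SD |
| Binary variable, 50% prevalence, n = 96 | 14 percentage points |
| Binary variable, 20% prevalence, n = 96 | 11 percentage points |

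**4. One prognostic covariate (simulated).** Logistic retention model, 96 per arm, 4,000 trials per row. The covariate log odds ratio per SD is assumed. The triggered rule adds the covariate only if its balance test is significant at 5%.

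| Retained, control v M-ROCC | Covariate log OR | Unadjusted | Triggered | Always adjusted |
|---|---|---|---|---|
| 67.5% v 77.5% | 0.5 | 32.7% | 32.8% | 34.8% |
| 67.5% v 77.5% | 1.0 | 32.7% | 32.3% | 37.9% |
| 67.5% v 77.5% | 1.5 | 33.5% | 33.7% | 43.0% |
| 60% v 80% | 0.5 | 86.2% | 86.4% | 88.0% |
| 60% v 80% | 1.0 | 85.6% | 86.2% | 90.8% |
| 60% v 80% | 1.5 | 85.7% | 86.7% | 94.1% |

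The first pair of rates is the midpoints of the dropout ranges, so it describes dropout from intervention rather than the active-prescription definition of retention.

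**5. Five prognostic covariates (simulated).** About 70% retained overall, treatment log odds ratio 1.0, 4,000 trials per row.

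| SD of covariate linear predictor | Unadjusted | Triggered | Always adjusted | Gain over triggered |
|---|---|---|---|---|
| 1.0 | 74.2% | 74.8% | 80.8% | 6 points |
| 1.4 | 65.6% | 66.1% | 77.4% | 11 points |

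A separate run with strong covariates gave 77% v 84% and 68% v 80%, gains of 7 and 12 points. With a linear-predictor SD of 0.5 the gain is about 1 point.

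**6. Type I error.** In the five-covariate setting it is 4.3-4.5% under the triggered rule and 4.8-5.1% when always adjusting.

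**7. Room for covariates.** Lowest expected discontinuations: 96 × 0.17 + 96 × 0.21 = 16.3 + 20.2 = 36.5. Highest: 96 × 0.28 + 96 × 0.44 = 26.9 + 42.2 = 69.1. That is about 36-69 events, which supports around five covariate parameters but not ten or more.

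**The case against.** Much of the case on the other side stands, and it limits the point.

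- **The significance test is stated only for the other variables.** A reader might infer that the ten known predictors pass as balanced up to 0.28 SD, or that ten 5% tests would raise at least one false flag in 40% of trials (1 - 0.95^10). The text attaches no test to those ten. Their defect is an undefined trigger. Steps 4 and 5 illustrate one plausible way of applying it. Under the reading that admits all ten once any is flagged, a simulation with a linear-predictor SD of 1.0 gave 78.7% v 82.8%, a gap of about 4 points.
- **A missed-imbalance rate is not meaningful here.** Quoting the test's power against a true imbalance of, say, 0.20 SD presupposes a systematic difference that randomisation excludes.
- **The 10% standardised difference is not the plan's standard for the randomised arms.** Section 9.6 uses it to choose a propensity score method ("We will select methods providing the best covariate balance across potential groups, graphically (range/density) and empirically") for self-selected groups. With 96 randomised per arm, a covariate exceeds 0.10 SD by chance about 49% of the time.
- **Error is not inflated overall.** In simulated trials with no flagged covariate but a risk-score imbalance beyond 1.5 standard errors (about 7% of trials), error was 9-13% under the rule and 5-6.5% when always adjusting. These figures rest on roughly 280 trials each and do not support a claim of doubled type I error.
- **The size rests on assumptions.** The dropout midpoints imply a log odds ratio of about 0.51, half the 1.0 used in step 5. At 0.5, power was only 22-34% under every rule. The simulated models also omit scheduling acceptability and the week 1-4 covariates.
- **Unblinded analysts add limited risk**, because the rule looks at baseline data and not at outcomes.

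None of this gives a reason to prefer an imbalance trigger over prespecified adjustment.

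**Conclusion.** The concern holds as a minor point. The plan makes adjustment for its own named predictors depend on an undefined chance imbalance, and adjustment for other variables depend on a significance test. The result is a data-dependent model with about the power of an unadjusted one. The loss against fixed adjustment is about 1 point of power with weak covariates and about 6 to 12 points with strong ones. That range assumes a linear-predictor SD of 0.5 to 1.4, a treatment log odds ratio of 1.0, 96 per arm, and a 5% test as the trigger. The documents give no covariate strengths, so the direction is firm and the size is illustrative.

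The loss is one of precision. A reader might infer bias or a raised false-positive rate. Imbalance under blocked 1:1 randomisation is chance, and overall type I error stays at or slightly below 5%, so neither follows. The primary outcome, the secondary outcomes and the sample size are unaffected.

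**What to change.** In section 9.6, delete both imbalance triggers. State instead that the retention logistic model and the Cox model adjust, whatever the observed balance, for a short fixed set of baseline predictors from the plan's list, chosen before unblinded outcome data are seen. Keep the set to about five parameters. Include scheduling acceptability alongside it, as section 4.3 already intends.

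Draw the set only from variables confirmed as collected. Candidates are age, psychiatric diagnosis from CAT-MH, childhood trauma from the ACE questionnaire, and baseline cocaine use from the oral fluid test or PhenX. The instrument descriptions in section 10.1 do not name hepatitis C, injection drug use history or previous opioid treatment, so these should be used only once their source is confirmed.

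Describe baseline balance by standardised differences without tests. Handle an unlisted variable that turns out to be imbalanced in a sensitivity analysis.

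The cost is a wording change, a check of which variables are held, and a few degrees of freedom.

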During this screening process, all eligible participants will need to rate the level of scheduling accessibility of the study groups days and times for both M-ROCC and the control group times being offered. Scheduling acceptability for assigned group will also be used as a covariate in statistical analyses.

If the participant is not excluded based on diagnosis, then they will be scheduled to complete the baseline survey and behavioral measures. If the participant has exclusion criteria on diagnostic assessments or cannot complete baseline measures, then the participant will not be eligible for randomization. Since participants with opioid use disorder often have transient mental health symptoms or intoxication related to recent substance use, participants with transient symptoms related to recent substance use will be able to wait for a re-review of eligibility after 30 days.

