### Administration

Participants will be enrolled on a rolling basis in preparation for their randomization to either the live-online M-ROCC or live-online control arm. Initially, randomization will only occur once 24 patients are ready for randomization. Following this initial group, every 4 weeks if at least 24 participants have completed baseline measures and are ready to start a group, they will be randomized using randomly selected block sizes of 4, 6 and 8 with a 1:1 ratio (24 weeks of live online M-ROCC : 24 weeks of live online control group). Next, after randomization, the participant will be informed about their assignment and given a start week for group sessions (either live online control or live online M-ROCC LDM) and will be given information about the group and its structure with a start date scheduled. We will aim to recruit constantly, with a new M-ROCC and control group beginning every 4-5 weeks.

We will aim for participants to begin attending control or LDM groups as soon as possible after randomization, but at least within 4 weeks. The study timeline will start

with week 1 being the first week the participant is assigned to start the study assigned group. Participants will continue to participate in standard care at each site while awaiting randomization and group placement, as well as throughout their enrollment in the study. For both study arms, participants will verify their presence with the group leader or research coordinator who will take attendance each week, which will be transferred to REDCap by the research coordinator after group.

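### The exploratory retention and time-to-discontinuation models adjust for buprenorphine non-adherence and illicit opioid use measured after randomisation, so they do not estimate the effect of assignment

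*Combined protocol and SAP*

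**What the plan says.** Section 1.3 sets an exploratory aim: the impact of M-ROCC randomisation status (and of practice dose) on intervention retention at 24 weeks. Section 9.5.2 lists retention and time to intervention discontinuation as the first two exploratory clinical outcomes, and weekly reports of buprenorphine non-adherence as the third.

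Section 9.6 (Exploratory analyses) gives the models. Retention is "defined as having an active BUP prescription in the past 28 days at the 24-week study visit". Covariates are introduced in three steps:

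- A named list of prognostic factors: "In the chance case of imbalance of assignment, we will add the following variables as measurable covariates in regression models".
- Further baseline variables: "We will also add any other baseline characteristics that may be significantly imbalanced after randomization".
- On-treatment data: "We will also include key data collected during the first 4 weeks of the intervention, i.e., BUP non-adherence, self-reported illicit opioid use".

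The Cox model then inherits these, "comparing hazard rates across the intervention and control groups, adjusting for the covariates described above in the logistic regression".

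Section 5.1 (Administration) defines the study clock, "with week 1 being the first week the participant is assigned to start the study assigned group", and has groups begin after randomisation.

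**The concern.** Weeks 1-4 are spent in the assigned LDM or control group. Use and adherence in those weeks can be affected by the arm and can in turn affect whether the participant stays in treatment. A model that holds them fixed answers a different question from the one in section 1.3, and one listed outcome (non-adherence) is being used to adjust another (retention).

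Two things can go wrong. If the arm changes early use or adherence, the part of its effect that runs through them is taken out of the reported ratio. And if something unmeasured drives both early use and retention, conditioning on early use links that factor to the arm. The remaining coefficient is then not a clean direct effect either.

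The Cox model has an added difficulty. No time origin or landmark is stated. If time runs from randomisation or week 1, a participant who stops during weeks 1-4 enters with covariates that are missing or partly collected after the event.

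**Working it through.** **The plan's own figure.** The only stated power is above 80% for the primary outcome (section 9.2). Design effect: 1 + (24 − 1) × 0.01 = 1.23. Effective size: 192 / 1.23 = 156.1, or 78 per arm. Effect: 0.56 / 1.25 = 0.448, rounded to 0.45. Two-sided power at 0.05 by the normal approximation is 80.2%. It reproduces. No effect or power is stated for retention or discontinuation, so the check below concerns what the adjusted models estimate.

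**Check 1: how the loss depends on an early arm effect.** The documents give no week 1-4 figures, so this model is assumed throughout. A is the arm, M is early illicit use, and L is a standard normal shared cause.

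- logit P(M = 1) = −0.2 + aA + 0.6L
- logit P(retained) = 0.9 + 0.25A − 1.6M − 0.4L
- loss = 1 − ln(OR with M) / ln(OR without M)

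| a | Early use, control vs M-ROCC | OR without M | OR with M | Loss |
|---|---|---|---|---|
| −0.8 | 45% vs 28% (17 points) | 1.59 | 1.23 | 56% |
| −0.4 | 45% vs 36% (9 points) | 1.40 | 1.25 | about a third |
| −0.2 | 45% vs 41% (about 5 points) | 1.31 | 1.26 | 14% |
| 0 | 45% vs 45% | 1.22 | 1.28 | none |

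First row: 1 − ln(1.228)/ln(1.590) = 1 − 0.205/0.464 = 0.56. The second row is 33% by simulation and 34% by numerical integration. In the last row the odds ratio rises because odds ratios are not collapsible over a prognostic variable; that is not bias.

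For scale, the means assumed in section 9.2 for weeks 13-24 imply 1 − 4.67/6 = 22.2% positive tests in M-ROCC and 1 − 4.11/6 = 31.5% in control, a gap of 9.3 points. That is per test and in a later period, so it is only a rough guide.

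**Check 2: at the plan's dropout figures.** Section 9.2 expects intervention dropout of 17-28% (M-ROCC) and 21-44% (control). The midpoints are 22.5% and 32.5%. Used as a stand-in for non-retention, they give OR = (0.775/0.225) / (0.675/0.325) = 3.444 / 2.077 = 1.66, a difference of 10 points. Assume M is 40% in control, and that M lowers the odds of retention by a factor of 2 to 4:

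- M 40% in both arms: adjusted OR 1.67-1.72, standardised risk difference still about 10 points.
- M 40% vs 30%: OR 1.54-1.46, difference 8.4-6.8 points.
- M 40% vs 20%: OR 1.44-1.25, difference 7.0-4.0 points. At the factor of 4 and 96 per arm, simulated power falls from about 31% to 10%.
- M 40% vs 20%, factor 4, plus an unmeasured shared cause: OR 1.12, difference 1.9 points.
- No arm effect on retention, M 40% vs 20% with no effect of its own, plus a shared cause: OR 0.86 where the truth is 1.00.

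The last case shows that the error is not only attenuation. There the shared cause raises use and lowers retention while M-ROCC lowers use, so the bias runs against M-ROCC. Reverse the arm's effect on early use and it runs the other way.

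**The case against.** The strongest reply is that nothing in the documents shows an early effect. Section 9.2 places the primary comparison from 12 weeks after assignment. Entry requires at least 4 weeks on a stable buprenorphine dose. Weeks 1-4 are the introductory stage, and the first weekly survey looks back over a week that may partly precede the first session. With no early effect, both checks show no attenuation. This stands: the loss is possible, not established. It does not justify the adjustment, because the plan cannot know beforehand that the early effect is nil, and sections 2.2 and 5.1 describe the early stage as meant to build engagement and prevent early dropout.

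One might also read the week 1-4 sentence as applying only under chance imbalance. That does not help. An arm difference in data collected after randomisation is not a baseline imbalance and may be the treatment effect itself.

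A reader might infer more than the text supports on three further points:

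- **Group variables.** Section 9.6 says it will collect "interpersonal variables related to the group as potential covariates or mediators". It does not place them in the retention or Cox model.
- **Significance-driven selection.** The significance wording applies to additional baseline characteristics, not to the named list. A fixed list is preferable, but that is a separate and lesser matter.
- **Scheduling.** Section 4.3 says: "Scheduling acceptability for assigned group will also be used as a covariate in statistical analyses". Ratings for both arms' group times are collected before randomisation, so this is not an on-treatment covariate, and no bias from it has been shown.

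**Conclusion.** The point holds for two exploratory models. As written, the logistic and Cox comparisons condition on post-randomisation variables and do not estimate the effect of randomisation status. The section names no direct-effect or mediation target, no landmark, and no companion model without these variables.

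The numerical consequence depends on an early arm effect that the documents do not give. It runs from no attenuation to a loss of somewhat over half of the log-odds effect in the 17-point scenario. That scenario is generous beside the 9-point gap implied for weeks 13-24, and its assumed retention (54% and 65%) lies below the 56-79% and 72-83% implied by the plan's dropout ranges.

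It would be tempting to say that the plan removes the treatment effect, or that the trial's main result is at risk. Neither follows. The week 1-4 sentence does not touch the primary GEE, the main secondary outcomes or the sample size, and both affected outcomes sit in an exploratory family of 15. The point is worth correcting but is not critical to the trial's main conclusions.

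**What to change.** In section 9.6, remove the week 1-4 variables from the logistic and Cox models that estimate the arm effect, and adjust only for pre-randomisation covariates. Suitable ones are already collected, for example past-30-day use from the PhenX core at screening (section 10.1) and the baseline oral fluid result (Table 1a). State the time origin of the Cox model.

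Keep the week 1-4 data for one of two uses: as auxiliary variables in the imputation model, or in a separately labelled mediation or week-4 landmark analysis that does not claim to estimate the effect of assignment.

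The cost is SAP wording only. No data collection, sample size or visit schedule changes.

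### In the exploratory dose analysis, session counts and 24-week practice minutes overlap the weeks 13-24 abstinence outcome, so relapse can lower the dose and results can be biased towards benefit

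*Combined protocol and SAP*

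**What the plan says.** The last paragraph of Section 9.6 (Exploratory analyses) sets out a non-randomised look at dose and at the intensive course. M-ROCC participants who join MTPC are followed, "tracking their 24-week outcomes compared to the control arm that receives no mindfulness and participants that only did LDM". Four exposure measures are named: number of sessions, "total practice mins during 24-weeks", at least 12 group sessions, and MTPC participation. Only practice minutes carry a stated period. The two session measures have no cut-off week, and no attendance rule is set for control participants.

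The paragraph accepts that continuers will probably differ at baseline. It relies on propensity scores (weighting, matching or sub-classification), saying that this "allows us to minimize bias by balancing the MTPC, LDM only, and control groups on observable intervention eligibility criteria" and on possible confounders of the outcome. The covariates are not listed.

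Elsewhere:
- Section 9.5.1 counts abstinent two-week periods in weeks 13-24, with a maximum of six.
- Section 5.1 describes MTPC as 16 weekly sessions after 4 to 8 weeks of the introductory course (LDM), and expects about half of the M-ROCC arm to start MTPC within 8 weeks. The Précis also allows an 8-week format.
- Section 8 lists worsening substance use that needs a higher level of care as a reason for leaving the group. Section 5.1 (Administration) lets participants leave M-ROCC when their risk level changes.

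**The concern.** A dose measure explains an outcome only if the dose comes first. Here much of the dose accrues while the outcome is being counted. A participant who relapses in week 15 may stop attending, by the protocol's own discontinuation routes, and then has both fewer abstinent periods and fewer sessions. Section 10.1 describes the practice diary as completed while the participant attends groups, so recorded minutes can fall for the same reason. The outcome then drives the exposure.

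Propensity scores built on baseline differences cannot remove this, because the disturbance arises after baseline. Adding weeks 1-12 data would not remove it either while the dose keeps running to week 24.

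At stake is the reading of dose. Practice dose is a stated exploratory aim (Section 1.3), and an apparent gradient could be credited to mindfulness training when it partly reflects staying abstinent.

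**Working it through.** **The plan's own figures.** No power or error rate is given for this exploratory analysis. The figures that can be reproduced concern the randomised comparison in Section 9.2, which assumes "a type I error of 0.05, a two-sided comparison, and a design effect of 1.23 derived from an ICC of 0.01".
- Design effect: 1 + (24 − 1) × 0.01 = 1.23. Effective size: 192 / 1.23 = 156.1, or 78 per arm.
- Planned difference: 4.67 − 4.11 = 0.56 of six tests. Pooled SD: √[(1.23² + 1.27²)/2] = 1.25. d = 0.56 / 1.25 = 0.448.
- Power at d = 0.45: 0.45 × √(78/2) − 1.96 = 0.85, giving 80.2% (79.7% by t-test). This agrees with the stated figure to rounding.
- MTPC starters: 47% of 96 = 45.1, matching the 45 in the Précis.

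**Overlap by calendar.**
- 16-week MTPC starting in week 5 runs to week 20: 8 of 16 sessions fall in weeks 13-24, and the 12th MTPC session is in week 16.
- 16-week MTPC starting in week 9 runs to week 24: 12 of 16 sessions overlap, and the 12th is in week 20.
- 8-week MTPC starting in week 5 or 9: 0 or 4 sessions overlap.
- If LDM sessions count, 12 weekly sessions by week 12 requires perfect attendance.
- MTPC entry in week 5 or 9 precedes week 13 and does not itself overlap.

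**What a residual bias does.** For 45 starters against 96 controls, the standard error in SD units is √(1/45 + 1/96) = 0.181. With a bias of b SD and no true effect, the chance of a favourable significant result is Φ(b/0.181 − 1.96): 2.5% at b = 0, 8% at 0.1, 20% at 0.2, 38% at 0.3.

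**Simulation with no true effect** (96 per arm, 1,500 runs per scenario; nominal favourable rate 2.5%). The assumptions are not from the documents. A latent stability score raises abstinence by 1.0 log-odds per SD. Where there is selection, it also raises joining and attendance by 0.7 per SD. One baseline covariate captures 100%, 50% or 10% of it. Feedback is the added log-odds of attending in an abstinent period. Entries are favourable significant results.

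| Selection measured | Feedback | Sessions over 24 weeks, covariate adjusted | Sessions to week 12, adjusted for baseline and early abstinence | At least 12 sessions v control, weighted (mean bias, periods) |
|---|---|---|---|---|
| No selection | 0 | 2.7% | 2.5% | 2.4% (0.01) |
| Fully | 0 | 1.6% | 1.3% | 1.7% (−0.01) |
| No selection | 0.8 | 39% | 2.5% | 1.7% (0.08) |
| Fully | 0.8 | 44% | 3.6% | 3.0% (0.06) |
| Half | 0 | 98% | 65% | 53% (0.39) |
| Half | 0.5 | 100% | 70% | 50% (0.36) |
| 10% | 0 | 100% | 90% | 93% (0.72) |

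Rows 3 and 4 isolate the overlap: stopping dose at week 12 brings 39-44% back to about nominal. The last three rows show unmeasured selection, which the cut-off does not cure. Weighted MTPC joiners against control gave 0.5-0.9% with selection fully measured, 10-12% with half and 25% with 10%. That is selection, not overlap.

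**Stronger feedback.** With assumed attendance of 85% in abstinent and 45% in other periods, the feedback is ln(0.85/0.15) − ln(0.45/0.55) = 1.73 + 0.20 = 1.94 log-odds. A separate null simulation on that basis gave false favourable 24-week dose-response results in 97-100% of trials, against about 3% for dose to week 12 adjusted for baseline and weeks 1-12 abstinence. At the 12-session threshold the bias was only 0.02-0.13 periods, or 4-23% of 0.56, and it vanished without feedback. The threshold discriminates little at these rates: expected attendance is 0.45 × 24 = 10.8 sessions if never abstinent and 0.85 × 24 = 20.4 if always abstinent.

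**Restricting both arms to week-12 attenders.** When attendance follows the same process in both arms, favourable results occurred in 0.4-2.6% of runs. With lower control attendance (assumed, for example, 75%/30% or 70%/25%), the null comparison was biased by −0.07 to −0.17 periods.

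**The case against.** The analysis is exploratory and openly naturalistic. It concedes selection and plans propensity methods, and matching could pick out comparable controls. The covariates are not confined to baseline, and the retention model in the same section already uses first-four-week opioid use and buprenorphine non-adherence. The paragraph refers to 24-week outcomes without naming the abstinence count, and the anxiety and pain scales are measured at week 24, so the overlap has to be inferred. At the plan's own 12-session threshold the feedback bias is small. A week-12 cut-off discards 8 or 12 of 16 weekly sessions, although the stated interest is in training beyond 8 weeks.

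Much of this stands and narrows the point. A reader might infer that every exposure runs over 24 weeks; MTPC entry does not, since it is mostly expected by week 8. A reader might infer that attenders are set unadjusted against the whole control arm; the plan balances three groups, one of them LDM-only. A reader might infer that this is the only evidence on dose; Section 1.3 and the false-discovery families for formal practices, informal practices and resource use also concern it.

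What does not fall is the overlap for session counts and practice minutes. No choice of covariates removes it while the dose runs into the outcome window, and nothing in the paragraph excludes the primary abstinence outcome.

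**Conclusion.** The point holds for the cumulative measures (number of sessions, at least 12 sessions, 24-week practice minutes) when the outcome is abstinence in weeks 13-24. Those results can be biased towards benefit. It is tempting to say that the analysis will show a benefit when there is none. The documents do not support that: they quantify neither feedback nor unmeasured selection, and under the assumptions tried the favourable false-positive rate for 24-week session dose ran from about nominal to almost certain.

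The part due to overlap alone was 39-44% at feedback of 0.8 log-odds, and 0.02-0.13 periods at the 12-session threshold under the 85%/45% assumption. Practice minutes and the LDM-only contrast were not simulated; for them the conclusion rests on the timing argument. MTPC entry by week 8 or 9 is largely free of the overlap but still open to selection. The intent-to-treat primary analysis is unaffected.

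**What to change.** Amend the dose paragraph of Section 9.6:

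1. For the weeks 13-24 abstinence outcome, define dose (sessions, practice minutes, MTPC started) from weeks 1-12 only.
2. Adjust or weight for baseline covariates plus weeks 1-12 toxicology and self-reported use. For MTPC entry, use only data from before entry, because later data may already reflect the course. Do not put attendance in the propensity model when attendance is the exposure.
3. As a sensitivity analysis, compare with control participants who meet the same week-12 attendance rule. State that this can be biased if attendance differs by arm, as Section 9.2 suggests it may: expected intervention dropout is 17-28% in M-ROCC and 21-44% in control.
4. Label any 24-week cumulative dose result as an association only.

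No new data are needed. Tables 1a and 1b already schedule oral fluid tests at baseline and weeks 4, 8 and 12, with weekly surveys and diaries, and attendance is taken weekly. The cost is wording and a narrower question: sessions after week 12 no longer count as dose in the week-12 analysis, and unmeasured selection remains and should be stated as a limitation.
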